9.5. Patient-reported Outcomes

The EORTC QLQ-C30, select items from the EORTC QLQ-MY20, and the EQ-5D-5L are included to assess subject's report of symptoms, functioning, and HRQoL.

The EORTC QLQ-C30 includes functional scales (physical functioning, role functioning, emotional functioning, cognitive functioning, and social functioning), symptom scales (fatigue, nausea and vomiting, and pain), and a Global Health Status scale ([Attachment 8](#)). Reliability, validity, and clinically meaningful change have been demonstrated among patients with MM (Wisloff 1996³⁷, Wisloff 1997³⁸). The EORTC Multiple Myeloma Module (QLQ-MY20) has been designed to use alongside the EORTC QLQ-C30 as a validated MM measure (Cocks 2007⁴). Only the 3 questions in the future perspective scale and the 6 questions in the disease symptoms scales will be administered ([Attachment 9](#)). The EQ-5D-5L is a generic preference-based measure of health status ([Attachment 10](#)). The 5-item questionnaire assesses mobility, self-care, usual activities, pain/discomfort and anxiety/depression to compute a single utility score plus a visual analog scale rating "health today" (Herdman 2011¹⁰).

PRO endpoints are to be assessed during the screening window, the Active Monitoring/study treatment phase, during pre-PD follow-up, at the time of disease progression, and during post-PD phases. PRO data collection during the Screening Phase will serve as the baseline score, to be collected after the subject signs informed consent. PRO assessments should be administered prior to any interventions that could influence subject perceptions of their health state, scheduled for the same day as PRO assessments are collected. The goal of data collection during the Active Monitoring/study treatment phase is to measure changes in emotional functioning due to receiving or not receiving treatment and to measure the impact of adverse events from daratumumab treatment on HRQoL. The goal of data collection during the pre-PD phase is to measure HRQoL after treatment and the value of potentially being in a pre-PD state longer because of treatment. The goal of data collection during the post-PD phase is to measure the onset and severity of symptoms associated with MM. Subject burden related to completion of PRO measures was a key consideration in determining the number of assessments as well as the timepoints likely to observe potential change in scores. If no in-person visit is scheduled, PROs can be interviewer-administered during tele-health (conducted via phone or video conference) visits.

9.6. Medical Resource Utilization

Medical resource utilization data associated with medical encounters (including tele-health visits [conducted via phone or video conference]), will be collected in the eCRF by the investigator and study-site personnel for all subjects at the disease assessment visits and at Months 3 and 6, post-PD. Protocol mandated procedures, tests, and encounters are excluded. The data collected will be

used to conduct exploratory analyses that may be used to support the value story and cost-effectiveness modelling for market access. The data collected include:

- Number and characteristic of diagnostic and therapeutic tests procedures (inpatient and outpatient)
- Number and duration of hospitalization (total length of stay [days], including duration by each hospital unit (intensive care unit)
- Outpatient medical encounters (including physician, nurse practitioner or emergency room visits, tests and procedures)

Please see eCRF completion guidelines for more details.

9.7. Safety Evaluations

Details regarding the IDMC are provided in Section 11.12. Safety will be measured by adverse events, physical examinations, ECGs, SC injection-site evaluations, clinical laboratory test results (hematology and chemistry), and ECOG performance status. All toxicities will be graded according to the NCI-CTCAE Version 4.03. Any clinically relevant changes occurring during the study must be recorded on the Adverse Event section of the eCRF. Any clinically significant abnormalities persisting at the end of the study/early withdrawal will be followed by the investigator until resolution or until a clinically stable endpoint is reached.

Based on the previous human experience with daratumumab, in vitro studies, and animal toxicological findings, IRRs/allergic reactions, hemolysis, and thrombocytopenia will be closely monitored. As a biologic agent, immunogenicity also will be monitored. Any of the safety monitoring assessments may be performed more frequently, and adverse events should be evaluated by the investigator according to the standard practice, if clinically indicated.

The study will include the following evaluations of safety and tolerability according to the time points provided in the Time and Events.

Adverse Events

Adverse events (with the exception of progression to MM) will be reported by the subject (or, when appropriate, by a caregiver, surrogate, or the subject's legally designated representative) as specified in the Time and Events Schedule ([Table 1](#)). Adverse events will be followed by the investigator as specified in Section 12, Adverse Event Reporting.

Clinical Laboratory Tests

As per protocol Amendment 6, central laboratory assessments will be discontinued.

Local Laboratory Testing

For subjects in the daratumumab arm, blood samples for serum chemistry and hematology will be collected as outlined in the Time and Events Schedule and analyzed by the local laboratory before each dosing to determine if the subject meets daratumumab treatment criteria described in Section 6.5. The investigator must review the laboratory results, document this review, and record

any clinically relevant changes occurring during the study in the adverse event section of the eCRF. The laboratory reports must be filed with the source documents. Local laboratory data must be entered in the eCRF for safety evaluation.

The following tests will be performed by the local laboratory:

- Hematology Panel
 - hemoglobin
 - White blood cell count, absolute neutrophil count, and absolute lymphocyte count
 - platelet count
- Serum Chemistry Panel
 - AST
 - ALT
 - total bilirubin^a
 - alkaline phosphatase
 - sodium
 - potassium
 - creatinine
 - glucose
 - blood urea nitrogen or urea
 - calcium and albumin-adjusted calcium
- Hepatitis B Virus (HBV) serology and DNA Tests
 - HBsAg, Anti-HBs, and Anti-HBc;
 - HBV DNA by PCR for patients with serologic evidence of past HBV infection (all patients during screening, arm B patients only Q12W during treatment, at the End of Treatment Visit, and Q12W for up to 6 months after the last dose of study treatment)

Serum or Urine Pregnancy Testing

- Serum or urine pregnancy testing at screening, and as clinically indicated, for women of childbearing potential only

HBV Serology

All subjects will be tested locally for hepatitis B surface antigen (HBsAg), hepatitis B surface antibody (Anti-HBs), and hepatitis B core antibody (Anti-HBc) at Screening. Additionally, subjects ongoing in the Treatment Phase (arm B only) who are within 6 months of starting study treatment when Protocol Amendment 3 is implemented will be required to have HBV serology performed locally upon signing the updated ICF. (Refer to Appendix 18.1 for specific requirements for France.)

HBV serology is not required at Screening or for subjects ongoing in the Treatment Phase (arm B only) who are within 6 months of starting study treatment if this was performed as part of standard of care within 3 months prior to first dose. For patients on treatment >6 months, testing is at investigator discretion.

HBV DNA Tests

Subjects who are positive for Anti-HBc or Anti-HBs will undergo testing for hepatitis B DNA by PCR. Subjects with serologic findings suggestive of HBV vaccination (Anti-HBs positivity as the only serologic marker) and a known history of prior HBV vaccination do not need to be tested for HBV DNA by PCR. During and following study treatment, subjects who have history of HBV infection (positive for Anti-HBc and/or Anti-HBs, have a negative HBV DNA PCR at baseline based on local laboratory assessments, and are randomized to Arm B) will be closely monitored for clinical and laboratory signs of reactivation of HBV as specified in the Time and Events Schedule ([Table 1](#)). Where required by local law, the results of HBV testing may be reported to the local health authorities.

Indirect Antiglobulin Test (IAT)

Blood Type, Rh, and indirect antiglobulin test (IAT) should be done before the first dose of daratumumab. Red blood cell (RBC) phenotyping (standard or extended) is an alternative to the IAT test, if required by a local standard.

Daratumumab interferes with the IAT, which is a routine pre-transfusion test performed to identify a subject's antibodies to minor antigens so that suitable donor blood can be given for transfusion. Daratumumab does not interfere with ABO/RhD typing. CD38 is expressed at very low levels on erythrocytes. Daratumumab binds to the CD38 on erythrocytes, which results in a positive IAT (Indirect Coombs Test). This positive result masks the detection of antibodies to minor antigens and may prevent or delay blood banks from issuing donor blood for transfusion. This effect occurs during daratumumab treatment and for up to 6 months after treatment ends. Subjects will receive a patient identification wallet card for the study that includes the blood profile (ABO, Rh, and IAT or phenotyping) determined before the first administration of daratumumab along with information on the IAT interference for healthcare providers/blood banks. Subjects are to carry this card throughout the treatment period and for at least 6 months after treatment ends. Blood banks can eliminate the daratumumab interference with IAT by treating reagent RBCs with dithiothreitol (DTT) ([Chapuy 2015](#)³).

Possible methods for blood banks to provide safe RBCs for transfusion to subjects receiving daratumumab include:

- Providing ABO/RhD compatible, phenotypically (standard or extended phenotyping) or genotypically matched units
- Providing ABO/RhD compatible, K-negative units after ruling out or identifying alloantibodies using DTT-treated reagent RBCs.

Uncrossmatched, ABO/RhD compatible RBC units should be administered if transfusion is needed emergently as per local blood bank practice.

Despite daratumumab binding to CD38 on erythrocytes, no indication of clinically significant hemolysis has been observed in daratumumab studies. For additional details, refer to the Daratumumab Investigator Brochure.

Electrocardiogram (ECG)

A 12-lead ECG will be performed as specified in the Time and Events Schedule. During the collection of ECGs, subjects should be in a quiet setting without distractions (eg, television, cell phones). Subjects should rest in a supine position for at least 5 minutes before ECG collection and should refrain from talking or moving arms or legs. If blood sampling is scheduled for the same time point as ECG recording, the procedures should be performed in the following order: ECG, blood draw.

Physical Examination and ECOG Performance Status

A complete physical examination (including neurological examination) should be performed during the Screening Phase. Thereafter, only a symptom-directed physical examination is required. Abnormalities will be recorded in the appropriate section of the eCRF. ECOG performance status will be used to evaluate the effect of the disease status on the activities of daily living. Height, and weight should be measured as clinically necessary and will be recorded in the eCRF at screening only. Vital signs should be monitored as clinically necessary. Only abnormal vital signs will be recorded in the eCRF, as part of AE reporting in the AE reporting page.

Pulmonary Function Test

Subjects with known or suspected COPD must have a FEV1 test, as specified in the Time and Events Schedule ([Table 1](#)). Refer to Section [6.3.2](#) of the protocol for details on subjects with higher risk of respiratory complications.

9.8. Sample Collection and Handling

The actual dates and times of sample collection must be recorded in the eCRF or laboratory requisition form. Refer to the Time and Events Schedule for the timing and frequency of all sample collections.

Instructions for the collection, handling, storage, and shipment of samples are found in the laboratory manual that will be provided. Collection, handling, storage, and shipment of samples must be under the specified, and where applicable, controlled temperature conditions as indicated in the laboratory manual.

10. SUBJECT COMPLETION/DISCONTINUATION OF STUDY TREATMENT/ WITHDRAWAL FROM THE STUDY

10.1. Completion

In the Active Monitoring group, a subject will be considered to have completed the study treatment if the subject has completed 36 months of Active Monitoring. In the daratumumab group, a subject will be considered to have completed study treatment if the subject has completed 39 cycles of therapy or 36 months of daratumumab, whichever occurs first. A subject will be considered to have completed the study (study completion defined in Section 17.9.1) if he or she has been followed to the end of the study or has died before the end of the study. Subjects who have been lost to follow-up, or have withdrawn consent for study participation before the end of the study, will not be considered to have completed the study.

10.2. Discontinuation of Active Monitoring (Arm A) or Study Treatment (Arm B)

Discontinuation of Active Monitoring (Arm A) or Study Treatment (Arm B)

A subject will not be automatically withdrawn from the study if he or she has to discontinue active monitoring or treatment before the end of the Active Monitoring or Treatment Phase. The End-of-Active Monitoring/End-of-Treatment Visit and Follow-up Visit assessments should continue as specified in the Time and Events Schedule ([Table 1](#)).

A subject must be discontinued from active monitoring or daratumumab treatment if:

- The investigator believes that for safety reasons or tolerability reasons (eg, adverse event) it is in the best interest of the subject to discontinue study treatment
- A subject randomized to Arm B becomes pregnant unless the subject (or the subject's legally acceptable representative), investigator, and sponsor agree the benefits outweigh the risks to the fetus and continuation of study treatment is in the best interest of the subject. A subject randomized to Arm A who becomes pregnant may remain on the study (refer to Section 4.3). For a pregnant subject who remains on the study, any study procedures deemed by the investigator to be potentially harmful to the fetus (eg, CT scans) may be deferred until the subject is no longer pregnant.
- The subject (or the subject's legally acceptable representative) withdraws consent for administration of study treatment
- The subject experiences unacceptable toxicity, including IRRs described in Section 6.4
- The subject's daratumumab dose is held for more than 28 days due to treatment-related adverse events (Arm B only)
- The subject experiences disease progression (definition see Section 9.2.2). [Biochemical progression without meeting IMWG diagnostic criteria for MM requiring therapy ([Table 9](#)) does not constitute a reason for discontinuation of therapy.]
- A subject who experiences a second primary malignancy that cannot be treated by surgery alone must be withdrawn from the study. However, a subject who develops a malignancy that may be cured surgically may continue to receive active monitoring (Arm A) or the assigned

study treatment (Arm B) and should continue to be followed for subsequent progression of MM.

Before subjects discontinue active monitoring (Arm A) or study treatment (Arm B) due to disease progression, sites will document disease progression by completing a disease progression form as soon as possible and within 48 hours of disease progression assessment. The medical monitor will confirm that treatment should be discontinued. After confirmation from the sponsor, active monitoring (Arm A) or study treatment (Arm B) will be discontinued and the subject will enter into Follow-up after completion of the End-of-Active Monitoring Visit or End-of-Treatment Visit.

The primary reason for discontinuation of active monitoring or study treatment is to be recorded in the eCRF.

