	Notes	Active Monitoring (Arm A; 12-week disease evaluations) / Treatment Phase (Arm B; 4-week treatment cycles after Cycle 6) ^a (up to 39 cycles or 36 months, whichever occurs first)						End of Active Monitoring/ End of Treatment	Pre-PD Follow-up	PD	Post-PD Follow-up	
		Screening (within 35 days before randomization)	C1-2		C3-6		C7-39					
		D1 ^b	D8	D15	D22	D1	D15	D1	30 (±3) days after the last Daratumumab dose ^c	every 12 weeks (±7 days)	at least every 6 months (until end of study)	
		Daratumumab (Arm B): Continuous from the time of signing of ICF until 30 days after last daratumumab dose, or until start of next therapy, whichever is earlier.										
Survival, Second primary malignancies		Throughout study until the end of study, and at a frequency of at least every 12 weeks until PD.										X
Best response to first-line MM treatment, PFS2	Investigator review; no central laboratory testing											X
Biomarkers Assessments. Per Amendment 6 all biomarker assessments by central lab are discontinued. FISH testing at PD to be performed locally.												
Whole blood (biomarkers)	Cytometry by time of flight	X	Week 24, Week 48, Week 96, and at suspected CR (±1 month with disease evaluations)					X		X		
	PBMCs	X										
	Plasma	X	Every 12 months from C1D1 (±1 month with disease evaluations)							X		
Stool (biomarkers)	Microbiome	X	Week 24 and at suspected CR (±1 month with disease evaluations)							X		
Bone Marrow aspirate ^m	Cytogenetics by FISH ^k	X								X		

Notes	Active Monitoring (Arm A; 12-week disease evaluations) / Treatment Phase (Arm B; 4-week treatment cycles after Cycle 6) ^a (up to 39 cycles or 36 months, whichever occurs first)						End of Active Monitoring/ End of Treatment	Pre-PD Follow-up	PD	Post-PD Follow-up
	Screening (within 35 days before randomization)	C1-2		C3-6		C7-39				
		D1 ^b	D8	D15	D22	D1	D15	D1		

- a. Treatment Phase (Arm B): daratumumab SC administered weekly in Cycles 1 and 2, every 2 weeks for Cycles 3 to 6, and every 4 weeks thereafter until 39 cycles or 36 months (whichever occurs first) or confirmed PD.
- b. C1D1 should occur within 5 days after randomization (Arm B).

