For subjects randomized to active monitoring (Arm A), no disease-specific treatment will be given and subjects are to be evaluated every 12 weeks. For subjects randomized to daratumumab (Arm B), daratumumab SC (daratumumab 1800 mg + rHuPH20 [2000 U/mL]) will be administered weekly in Cycles 1 and 2, then every 2 weeks for Cycle 3 to Cycle 6, and every 4 weeks thereafter until 39 cycles or up to 36 months or confirmed PD (or other reasons as outlined in Section 10), whichever occurs first. All subjects in the daratumumab group will be observed for at least 6 hours after the end of the SC injection during Cycle 1 Day 1 and, if deemed necessary by the investigator, after subsequent injections. Based on the data available as of October 2017 from Study MMY1004, no subject has had an IRR with an onset >6 hours after daratumumab SC injection (IB Daratumumab 2017 ¹¹). Measures to prevent IRRs include predose medication with methylprednisolone, paracetamol, and an antihistamine. Montelukast may also be added as a predose medication at the investigator's discretion. Methylprednisolone also will be administered after daratumumab administration with the intention of preventing delayed IRRs.

The Follow-up Phase will begin once a subject completes 39 cycles or 36 months (whichever occurs first) or discontinues active monitoring (Arm A) or daratumumab treatment (Arm B) and completes the End-of-Active Monitoring Visit (Arm A) or End-of-Treatment Visit (Arm B). In both groups, disease evaluation will continue every 12 weeks thereafter until disease progression, as indicated in the Time and Events Schedule (Table 1). The Follow-up Phase for each subject will continue until death, lost to follow up, consent withdrawal, or study end, whichever occurs first.

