9.1.4. Follow-Up Phase

The Follow-up Phase will begin once the subject completes 39 cycles or 36 months (whichever occurs first) of active monitoring (Arm A) or daratumumab treatment (Arm B). Reasons for premature discontinuation of active monitoring or daratumumab treatment are listed in Section 10.2. Subjects who discontinue before PD must continue to have disease evaluations as described in Section 9.2, until study completion or confirmed PD (or other reasons as outlined in Section 10). If subjects have not progressed to MM, then no other treatment for SMM or MM is allowed during the study. Follow-up for first-line MM treatment (including the response to first-line MM treatment), second primary malignancies, and survival status will be obtained as specified in the Time and Events Schedule (Table 1). Survival will be followed until the end of the study and at a frequency of at least every 12 weeks until PD. After PD, survival is to be followed at least every 6 months, until the end of the study.

If PRO or survival information is obtained via telephone contact, then written documentation of the communication must be available for review in the source documents. If the subject has died, then the date and cause of death will be collected and documented in the eCRF.

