10.3. Withdrawal from the Study (Arm A and Arm B)

A subject will be withdrawn from the study for any of the following reasons:

- Lost to follow-up
- Withdrawal of consent
- Death
- The study investigator, for any reason, stops the subject's participation in the study
- Sponsor terminates the study

If a subject discontinues active monitoring or study drug and withdraws from the study before the end of the active monitoring or treatment phase, End-of-Active Monitoring or End-of-Treatment Visit assessments should be obtained.

If a subject is lost to follow-up, every reasonable effort must be made by the study-site personnel to contact the subject and determine the reason for discontinuation/withdrawal. The measures taken to follow up must be documented.

When a subject withdraws before completing the study, the reason for withdrawal is to be documented in the eCRF and in the source document. Study drug assigned to the withdrawn subject may not be assigned to another subject. Subjects who withdraw will not be replaced. Additional subjects will not be enrolled. If a subject withdraws from the study, assessments in the End-of-Active Monitoring or the End-of-Treatment Visit should be obtained. If the reason for withdrawal from the study is withdrawal of consent, no additional assessments are allowed. Public record searches will be conducted, if permitted by local law.

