12.3.3. Pregnancy

All initial reports of pregnancy in female subjects or partners of male subjects must be reported to the sponsor by the study-site personnel within 24 hours of their knowledge of the event using the appropriate pregnancy notification form. Abnormal pregnancy outcomes (eg, spontaneous abortion, fetal death, stillbirth, congenital anomalies, ectopic pregnancy) are considered serious adverse events and must be reported using the Serious Adverse Event Form. Any subject who becomes pregnant during the study must be promptly withdrawn from the study and discontinue further study treatment unless the subject (or the subject's legally acceptable representative), investigator, and sponsor agree the benefits outweigh the risks to the fetus and continuation of study treatment is in the best interests of the subject. A subject randomized to Arm A who becomes pregnant may remain on the study (refer to Section 4.3). For a pregnant subject who remains on the study, any study procedures deemed by the investigator to be potentially harmful to the fetus (eg, CT scans) may be deferred until the subject is no longer pregnant. Because the effect of the study drug on sperm is unknown, pregnancies in partners of male subjects included in the study will be reported, as noted above. Follow-up information regarding the outcome of the pregnancy and any postnatal sequelae in the infant will be required.

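### Protocol 10.2 orders study withdrawal for some second primary malignancies inside a list about stopping monitoring or treatment; taken literally, this contradicts the section's own opening and the survival, second-malignancy and PFS2 follow-up

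*Protocol*

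**What the plan says.** Protocol 10.2 first states that a subject who has to stop monitoring or treatment early is not thereby withdrawn from the study, and that the end-of-phase visit and follow-up assessments continue under Table 1. It then gives a list introduced by "A subject must be discontinued from active monitoring or daratumumab treatment if". One bullet in that list says: "A subject who experiences a second primary malignancy that cannot be treated by surgery alone must be withdrawn from the study". The next sentence turns to surgically curable malignancies: such a subject may go on with monitoring or the assigned treatment and "should continue to be followed for subsequent progression of MM".

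Other places that bear on the bullet:

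- **Protocol 9.1.4:** "Follow-up for first-line MM treatment (including the response to first-line MM treatment), second primary malignancies, and survival status will be obtained" as Table 1 specifies, with survival followed to the end of the study.
- **Protocol Table 1**, row for survival and second primary malignancies: "Throughout study until the end of study, and at a frequency of at least every 12 weeks until PD". A separate row collects best response to first-line myeloma treatment and PFS2 after progression.
- **Protocol 3.1:** "The Follow-up Phase for each subject will continue until death, lost to follow up, consent withdrawal, or study end, whichever occurs first".
- **Protocol 10.3:** "A subject will be withdrawn from the study for any of the following reasons". The reasons are loss to follow-up, consent withdrawal, death, the investigator's decision for any reason, and termination by the sponsor. Second malignancy is not named.
- **SAP 5.1.1:** PFS2 and OS are tested in sequence after PFS and ORR, with 134 PFS2 events and 107 deaths expected at the final analysis.

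**The concern.** The list is about stopping monitoring or treatment, but the bullet prescribes leaving the study, which the protocol otherwise treats as a separate step. A site that follows the bullet ends scheduled contact. A site that follows the opening of 10.2 and Table 1 keeps the subject in follow-up. Subjects with the same event could therefore be handled differently.

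At stake is censoring of two alpha-controlled endpoints at a new cancer that needs more than surgery, an event plausibly related to the risk of death. Its frequency could also differ between the arms. After withdrawal before progression, later progression to myeloma, the start of first-line therapy and progression on that therapy would all go unrecorded. For PFS2, SAP Table 5 censors a living subject without progression on study at the last disease assessment, so later survival contact can add a death but adds no PFS2 time for someone still alive.

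**Working it through.** **Step 1: the texts side by side.**

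| Provision | Relation to the bullet read literally |
|---|---|
| Opening of Protocol 10.2 | Direct conflict: stopping is not withdrawal, and follow-up assessments continue |
| Protocol 9.1.4 and Table 1: survival, second malignancies, first-line treatment and PFS2 | Direct conflict: no exception for this event |
| Protocol 9.1.4 and 9.2: 12-weekly disease evaluations | No conflict: both allow them to end for Section 10 reasons |
| Protocol 3.1: four ends of follow-up | Weak conflict: that list also leaves out the investigator's decision, which 10.3 includes, so it is not complete |
| Protocol 10.3 | Weak conflict: the investigator item could cover the case, but it is discretionary and the bullet is not |

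**Step 2: what can still be recovered.** Public-record searches are planned where local law permits (Protocol 10.3), and consent covers survival information (Protocol 16.2.3). Known deaths count for OS (SAP 5.3.6.1) and for PFS2 (SAP 5.3.5.1). A malignancy reported as a serious adverse event is followed further (Protocol 12.3.2). None of these routes records progression on first-line myeloma therapy.

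**Step 3: how many subjects.** The plan has no figure to reproduce here.

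- Inputs from the plan: 180 subjects per arm, 24-month accrual (taken as uniform), median PFS 30 and 48 months, and a phase of at most 36 months.
- Assumptions: exponential PFS, no dropout, the bullet applies only before progression and within the 36 months, and 0.5 to 2 qualifying cases per 100 person-years.

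Mean time in the phase, once everyone has had the chance to reach 36 months, is (1 − exp(−36λ))/λ with λ = ln 2 / median.

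- Arm A: λ = 0.02310, mean 24.4 months; 180 × 24.4/12 gives 366.6 person-years before rounding the mean.
- Arm B: λ = 0.01444, mean 28.1 months; likewise 421.1 person-years.
- Total: 366.6 + 421.1 = 787.7 person-years.
- Cases: 787.7 × 0.005 = 3.9 and 787.7 × 0.02 = 15.8, so about 4 to 16.

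Stopping the count at month 48, the planned time of the primary analysis, gives 345.1 + 392.7 = 737.8 person-years. The remaining 787.7 − 737.8 = 49.9 person-years all fall before month 60 and carry 0.25 to 1.0 cases.

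**Step 4: how far the estimates could move.** This used a simulation with 1,000,000 subjects per arm, cutoff at month 96, and planned medians of 100 and 125 months (OS) and 72 and 96 months (PFS2). An extra death hazard was added after the malignancy (median 48 or 120 months). The Cox hazard ratio with censoring at withdrawal was compared with the one from full follow-up.

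- Equal rates, no deaths recovered: the hazard ratio falls by 0.002 to 0.013 for OS and by 0.0015 to 0.014 for PFS2.
- Assumed 1 (Arm A) against 2 (Arm B) per 100 person-years: 366.6 × 0.01 = 3.7 and 421.1 × 0.02 = 8.4 cases. The fall is 0.015 to 0.030 for OS and 0.0095 to 0.023 for PFS2.
- Worst OS case: 0.8304 to 0.8001, a log change of 0.037. Standard error 2/√107 = 0.193; ratio 0.19.
- Worst PFS2 case: log change 0.035. Standard error 2/√134 = 0.173; ratio 0.20.
- Worst OS case with survival recovered for half of those withdrawn: the fall is 0.0145.

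Repeat runs differ by about 0.001 in the hazard ratio.

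**The case against.** The strongest reply is that the bullet is only loosely worded. The opening of 10.2 governs the list. The sentence on surgically curable cases speaks first of continuing monitoring or treatment, so the intended contrast may be stopping against not stopping. The protocol uses the same phrase loosely elsewhere: for pregnancy, 12.3.3 says "Any subject who becomes pregnant during the study must be promptly withdrawn from the study and discontinue further study treatment unless the subject", while 10.2 lists pregnancy in Arm B as a reason to stop treatment. The second-malignancy listing in SAP 6.3.5, which includes any subsequent anti-cancer therapy, also suggests that data collection after the event was intended. All of this stands, and intent cannot be settled from the text. It does not remove the contradiction, because the bullet names the study, and its second half reserves continued follow-up for the curable cases.

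It also stands that much of the remedy is already planned: public-record searches, known deaths counted as events, and discontinuation reasons reported (SAP 4.2).

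The size is open to challenge too. The worst case needs a 2:1 excess in Arm B that no passage supports, and no deaths recovered. The model also adds malignancy deaths to planned OS medians that are already all-cause, which may count them twice: the full-follow-up hazard ratio rises to 0.83 and censoring merely returns it to the planned 0.80. The figures show an order of magnitude and do not estimate a bias.

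**Conclusion.** The inconsistency is real and minor. Followed literally, the bullet ends scheduled PFS2 and survival follow-up at a prognosis-related event and conflicts with the opening of 10.2, with 9.1.4 and with Table 1. On assumed rates it touches about 4 to 16 subjects and moves the log hazard ratio by at most about 0.2 standard errors, in a model that probably overstates the effect.

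A reader might infer three stronger things that the documents do not support:

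- **That OS or PFS2 is materially biased toward daratumumab.** No second-malignancy rate is given for either arm, and the shift is small even under adverse assumptions.
- **That outcomes are wholly lost.** Deaths are partly recoverable; the unrecoverable part is progression on first-line therapy.
- **That the bullet also contradicts the rules on disease evaluations, or plainly breaches 3.1 and 10.3.** Disease evaluations may end for Section 10 reasons, and the other two conflicts are weak.

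The Amendment 6 summary says that the primary PFS analysis has concluded. If the bullet applies only during the monitoring or treatment phase, few if any new cases remain. The practical interest now lies in subjects already withdrawn under it, before the final PFS2 and OS analyses.

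**What to change.** 1. Reconcile the bullet with the opening of 10.2, 9.1.4 and Table 1 so that this event alone does not end collection of survival, second-malignancy and PFS2 data. Have it state whether monitoring or treatment stops and whether the 12-weekly disease evaluations continue. Those decisions are the sponsor's, and no view is taken on them here.
2. For subjects already withdrawn under the bullet, show the number by arm within the disposition table planned in SAP 4.2. Retrieve survival status where consent and local law permit, and count known deaths under the existing OS and PFS2 rules.
3. Only if that number is not negligible, add one supplementary PFS2 and OS analysis addressing this censoring, with the same rule in both arms and labelled as added after the primary analysis.

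The cost is a wording amendment to one bullet, one extra line in a planned table and, conditionally, one supplementary analysis. The downside is a few more follow-up contacts with subjects who are being treated for another cancer.
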